UT-S/PMH and OHSU research team members will survey family members of trauma patients to compare the quality of communication for severely injured geriatric trauma patients cared for by trauma teams. When possible, UT-S/PMH and OHSU will survey patients on their quality of life. UT-S/PMH and OHSU will survey the patient’s primary nurse on the quality of communication patients and will survey patient’s families about their thoughts on the quality of communication as well. UT-S/PMH and OHSU will survey trauma unit staff before and after clinicians learn to use the best case/worst case tool, to assess whether the communication intervention improves feelings of moral distress. UT-S/PMH and OHSU will use chart review to collect downstream clinical outcomes including intensity of treatment and receipt of palliative care. UT-S/PMH and OHSU will archive de-identified graphic aids used by trauma surgeons with intervention patients to explore how the intervention was enacted.

Background and Significance

Improvements in medical care that have increased life expectancy have shifted the end-of-life trajectory for older adults who are now increasingly vulnerable to traumatic injury.¹ Each year, half a million older adults will suffer injury from a fall or car crash, making it the fifth leading cause of death. Older adults fare far worse than younger patients with similar injuries due to presence of chronic comorbid conditions and reduced physiologic reserve.²⁻⁴ Traumatic injury is often a terminal event that leads to a 20% in-hospital and 40% one-year mortality.⁵ Severely injured older adults undergo a series of invasive surgical interventions furthering a course of care—including prolonged life support³ or confinement in a nursing home—that is often inconsistent with patients’ preferences and goals. Given the burdens of treatment and poor prognosis, severely injured older adults would benefit from decision support interventions to facilitate early access to palliative care which can reduce unwanted invasive procedures, address symptoms and clarify long-term goals.^{6,7}

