Family members: Family members are the primary participants in this study and the primary outcome is family-reported quality of communication. We anticipate that few patients will be well enough or have decision making capacity (DMC) to participate. Patients will participate with a family member who is present and is a formally or informally designated decision maker. If a patient has DMC, they will be asked by a UT-S/PMH or OHSU research team member to designate a family member to enroll in the study as the “study partner”. Patients cannot be enrolled without a family member study partner as our primary outcome is the family member’s perception of the quality of communication. If a patient lacks DMC, their family member or surrogate decision maker will be identified and approached. In this circumstance, the surrogate decision maker and study partner do not have to be the same person; a surrogate decision maker may provide consent for the patient chart review and re-contact at 30 days if they have regained DMC whereas another family member serving as study partner may participate in the surveys. In this circumstance (where the study partner is the only one to have consented), if the patient is alive at 30 days, the study partner will complete 3 surveys (including the Trauma Quality of Life survey at 30 days). If they are deceased, the study partner will complete the first two surveys only.

Patients:

We will include traumatically injured patients 50 and older admitted to the ICU.

We will include both patients who have or lack DMC, as described in the “Consent and HIPAA Authorization” section. Given the nature of traumatic injury in the study patient population we anticipate few, if any, patients will have DMC.

Exclusion Criteria:

Trauma providers

Focus groups: Potential participants must not be on call at the time of the focus group.

Best case/worst case tool training and subsequent follow up interviews: We will exclude residents who have not had at least 5 years of postgraduate training. We will also exclude care providers who do not directly provide primary trauma care in the ICU. Trauma consultants including for example, neurosurgeons, orthopedic surgeons, otolaryngologists will be excluded from best case/worst case training.

Nurse survey: No exclusion criteria.

Moral distress survey: No exclusion criteria.

Patients and family members

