If a patient lacks DMC their surrogate decision maker will be approached or contacted regarding surrogate consent. This consent process will occur either face-to-face (if the family member providing surrogate consent is available locally) in which case written consent will be collected OR may be provided via phone or web survey (if the family member providing surrogate consent is out of the area), in which case verbal consent or consent via clicking a survey answer will be collected. In cases where the family member providing surrogate consent is not available locally, the first contact with them will always be made via phone, at which time they will be given the option of a verbal consent or web-based consent process.

Table: Consent and enrollment options

Patient has DMC

 • Patient wants to participate • Family member wants to participate as study partner 	Enroll patient and family member

 • Patient wants to participate • Family member does not want to participate as study partner 	Do not enroll in study

 • Patient does not want to participate • Family member wants to participate as study partner 	Do not enroll in study

Patient does not have DMC and LAR/surrogate is bedside

 • LAR wants to participate as both surrogate and study partner 	Enroll LAR as surrogate and study partner

 • LAR does not want to participate as surrogate or study partner and no other family member agrees to be study partner 	Do not enroll in study

 • LAR does not want to participate as surrogate • Another family member agrees to be study partner 	Enroll study partner. Do not enroll LAR/patient (no chart review or P1 data collected)

Patient does not have DMC and LAR/surrogate is not bedside/is out of area

 • LAR wants to participate as surrogate • Bedside family member wants to participate as study partner 	Enroll LAR as surrogate and family member as study partner

 • LAR does not want to participate as surrogate • Bedside family member wants to participate as study partner 	Enroll family member as study partner. Do not enroll LAR/patient (no chart review or P1 data collected)

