
 • LAR wants to participate as surrogate • Bedside family member does not want to participate as study partner 	Do not enroll LAR/patient or family member

 LAR does not want to participate as surrogate Bedside family member does not want to participate as study partner 	Do not enroll LAR/patient or family member
--	--

Definitions:

Patient consent: Patient with DMC consents to chart review and P1 survey

Study partner consent: A family member or caregiver present at bedside who consents to completing F1-F3 surveys. This person may or may not be the same as the surrogate LAR

[figure not shown]
Surrogate consent: In case of patient who lacks DMC, the appropriate surrogate decision maker or legally authorized representative (LAR) provides consent for patient chart review and for researchers to contact patient for P1 if they have regained DMC

Instruments

Instrument	Definition	When administered	How administered/obtained	Specific Measures
Focus group guide	Used in each focus group to guide discussion	During focus groups	Facilitator will draw on questions from the guide.	N/A
Interview guide	Used in interviews follow trauma provider training	Interviews with trauma providers following their BC/WC training	Interviewer will pose questions from the guide	N/A
F1: Family Survey 1	First survey administered to family member study partner	As close as possible to 72 hours after admission	In-person (if family member available in hospital) Telephone	QOC ⁴⁰ , family version Single Item Literacy Screener ⁵⁰ Family member demographics, including relationship with patient
N1: Nurse survey	Survey given to primary nurse for patient	As close as possible to 72 hours after admission	In-person Email/web survey	QOC ⁴⁰ , nurse version (During the intervention arm, this survey will contain several addition questions on whether the surgeon used best case/worst case. These

				will be submitted as part of a Change of Protocol)
F2: Family Survey 2	Second survey administered to family study partner	10 days post-admission	In-person (if family member available in hospital) Telephone	FICS ⁴¹ Goal Concordant Care ⁴²
F3: Family Survey 3	Third survey administered to family study partner	30 days post-admission	In-person (if family member available in hospital) Telephone	T-QoL ⁴³ , if patient is alive. If patient is deceased, no survey given

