Research team members at UT-S/PMH and OHSU will aim to collect the F2 survey 10 days after the patient's admission. The Family Inpatient Communication Survey (FICS)⁴¹ will be administered as part of this survey. This instrument is designed for family members of patients to measure communication and care coordination. FICS includes 30 questions, 18 of which assess information and 12 of which assess emotional support. Two additional survey questions taken from the SUPPORT study⁴² will also be asked, to assess goal concordant care. The family member surveys are independent; unless a family member withdraws their participation from the study, we will contact them to complete all surveys, regardless of whether they have completed prior ones.

Research team members will make multiple attempts to collect this data in person at 10 days after admission if the patient is still receiving care in the trauma unit and if the family member is available at the patient's bedside. If the family member cannot be reached in person or the patient is no longer receiving care in the hospital, research team members will reach out to them by phone and may complete the survey by phone.

F3: Family Survey 3 (for study partners)

Chart review conducted by research team members at UT-S/PMH and OHSU will be used to assess whether patients are alive and, if so, have DMC at 30 days.

If the patient is alive, a member of the research team will contact the enrolled family member to schedule a good time to conduct this survey over the phone or in person in the hospital setting, if the patient is still receiving care there. This F3 survey consists of The Trauma Quality of Life (T-QoL)⁴³ survey, adapted for reporting by family members. This 43-item survey is designed assess posttraumatic quality of life.

If the patient has died in between admission and 30 days post-admission, there is no third family survey.

P1: Patient Survey

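### Where only the study partner consents, does the day-30 family survey depend on a chart that may not be opened, and does the primary analysis lose these families?

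*Combined protocol and SAP*

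**What the plan says.** The consent and enrollment table (Consent and HIPAA authorization) has two rows in which the patient lacks decision-making capacity, the legally authorized representative declines to act as surrogate, and another family member enrols as study partner. For the patient both rows say "Do not enroll LAR/patient (no chart review or P1 data collected". The definitions below the table explain why. The surrogate is the person who "provides consent for patient chart review and for researchers to contact patient for P1", whereas the study partner is "A family member or caregiver present at bedside who consents to completing F1-F3 surveys".

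The inclusion criteria for family members cover the same group ("where the study partner is the only one to have consented), if the patient is alive at 30 days"): the partner then completes three surveys, or only the first two if the patient has died. They name no source for vital status.

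Under F3: Family Survey 3, the protocol says "Chart review conducted by research team members at UT-S/PMH and OHSU will be used to assess whether patients are alive", and then "If the patient is alive, a member of the research team will contact the enrolled family member to schedule a good time". It makes no exception for partner-only families. Under F2: Family Survey 2, it says that "unless a family member withdraws their participation from the study, we will contact them to complete all surveys".

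The primary outcome is the family-reported QOC in F1, at about 72 hours. The Analysis section specifies a mixed model with a treatment indicator, a surgeon random effect and site indicators, plus covariate adjustment for precision. It does not name the adjustment covariates for that model. Patient-level covariates such as injury severity are listed under Chart review. No analysis set or missing-covariate rule is stated.

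**The concern.** There are two strands.

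The first is procedural. For partner-only families, staff following the F3 procedure would open a chart that the surrogate did not authorise. Staff following the consent table have no written way to learn whether F3 is due. The consent waiver for record review does not help, because it covers pre-screening only. The sponsor planned for this group explicitly, so the case is not contrived.

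The second is analytic. If the QOC model adjusts for injury severity and other chart variables, and the software drops incomplete records, valid primary-outcome scores would be lost from people the protocol calls its primary participants. At stake would be some power. There could also be bias if surrogate refusal were related to how communication was experienced and this differed between the two periods.

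**Working it through.** **1. The F3 texts side by side.**

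| Place | Rule for partner-only families | Source of vital status |
|---|---|---|
| Inclusion criteria, family members | F3 if alive at day 30, otherwise F1 and F2 only | none named |
| Consent table and definitions | no chart review; partner consents to F1-F3 | not addressed |
| Instruments table, F3 row | F3 if alive | none named |
| F2 procedure | contact for all surveys unless withdrawn | not addressed |
| F3 procedure | contact if alive | chart review |

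Only one general sentence, in the F3 procedure, clashes with the specific bar in the consent table. The rules that make F3 due can be met by any source of vital status, and the partner has already agreed to be surveyed at day 30.

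**2. What the conflict touches.** F1 is collected weeks before day 30, so QOC is unaffected. The Analysis section tests QOC and gives treatment intensity and palliative care as examples of exploratory endpoints. The F3 measure is not named there. Vital status from the partner should match the chart, so the F3 data would be the same.

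**3. What the QOC model needs from the chart.** Period and site are known at enrolment, and so is the surgeon, because staff confirm eligibility with the enrolled provider. F1 itself collects family demographics and literacy. The core model and some adjustment therefore need no chart. For patients who decline, the protocol also keeps gender, race, age and GTOS (TRISS at ages 50-64). It does not say whether this covers a surrogate's refusal or could be linked to F1.

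**4. Size if the families were dropped anyway.**

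Inputs from Sample Size: 50 per arm, SD 3.5, effect 2.00, between-doctor share ρ of 10% or 30%. Two-sided 0.05 is assumed, since the plan states no alpha. Surgeon variance is removed because surgeons are compared with themselves before and after training.

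- Residual SD = 3.5 × √(1 − ρ), which is 3.320 at 10% and 2.928 at 30%.
- Noncentrality = 2.00 / (SD × √(2/n)), with 2n − 2 degrees of freedom.
- At n = 50: 2.00 / (3.320 × 0.2) = 3.012, power 84.7%; and 2.00 / (2.928 × 0.2) = 3.415, power 92.2%. The plan states 84% and 92%, so its figures are reproduced.

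| Families lost (assumed) | n per arm | Power, ρ = 10% | Power, ρ = 30% |
|---|---|---|---|
| 0% | 50 | 84.7% | 92.2% |
| 5% | 47.5 | 82.8% | 90.9% |
| 10% | 45 | 80.7% | 89.3% |
| 20% | 40 | 75.8% | 85.5% |

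Power reaches 80% at n = 44.25 (1 − 44.25/50 = 11.5% lost) for ρ = 10%, and at n = 34.64 (30.7% lost) for ρ = 30%.

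**5. Two reasons the table overstates the loss against plan.**

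- It uses the unadjusted SD, yet the loss arises only in an adjusted fit. Power depends essentially on n divided by residual variance. Covariates explaining 10% of that variance offset a 10% loss (45/0.90 = 50), and 5% offsets a 5% loss (47.5/0.95 = 50).
- The sample size counts patients, and in these two rows the patient is not enrolled. If partner-only families fall outside the 50 per arm, nothing is lost against plan.

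**The case for a change.** The strongest reply is that a consent boundary matters even for one family. The surrogate's refusal is explicit, the F3 text calls the vital-status check a chart review, and the definitions place chart review under patient or surrogate consent. A milder reading, in which only data abstraction is barred, does not fit those definitions. The P1 procedure lets staff check with the care team as well as the chart, but P1 is not collected here. Asking the partner is sensible but unwritten, and some calls would reach a bereaved relative. The Background says severe injury in older adults "leads to a 20% in-hospital and 40% one-year mortality". With an assumed 10 partner-only families among 100, applying those rates gives 10 × 0.20 = 2 to 10 × 0.40 = 4 deaths, although neither figure is a day-30 rate.

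This stands as a criticism of wording: the texts do not agree. It does not reach the statistics, because no estimate or stated figure depends on how staff learn vital status.

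On QOC, it is fair that offsetting a loss against the plan's unadjusted power does not recover the information an adjusted analysis of all families would have. It is also conceivable that a surrogate unhappy with communication declines more readily. But the documents give nothing with which to size either effect, and the harm comes from a complete-case fit that the plan neither prescribes nor implies. Both remedies carry a cost: leaving chart covariates out of the primary model gives up severity adjustment in a before/after comparison, while imputing them relies on few observed variables.

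**Conclusion.** The concern does not call for a change to the plan. The F3 strand is a genuine inconsistency between the consent table and one sentence of the F3 procedure. It is a matter of consent procedure in a survey the analysis section does not name. Staff can resolve it by asking the partner, who has already consented to F3. It leaves the F1 primary outcome, the power statement and the trial's conclusion untouched.

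The QOC strand is a missing detail that analysts would ordinarily fill by keeping every family with an F1 score. If they did not, power for 2.00 points would still exceed 80% at 5% or 10% loss under both of the plan's variance scenarios. In the 10% scenario it would fall below 80% only beyond about 11.5% loss.

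This rests on two-sided 0.05, on loss shares that are illustrative because the documents give none, and on partner-only families counting toward the 50 per arm. A much larger partner-only share, combined with a complete-case fit, would weaken the conclusion, but nothing in the documents points to either.

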The purpose of this study is to test the effect of the “best case/worse case” communication tool on the quality of communication with older patients admitted to two trauma units and to collect feedback on the tool to help adapt it to the trauma setting. The intervention was developed and tested with acute care surgical patients at the University of Wisconsin (UW) and the present study seeks to test whether the intervention will work in a different setting.

To adapt the tool to trauma settings, we will conduct focus groups at UW Health Oregon Health Sciences University (OHSU) and Parkland Memorial Hospital (PMH) at the University of Texas-Southwestern (UT-S). Because trauma care is delivered by a multidisciplinary team, we will include attending trauma surgeons, surgical residents, ICU nurses, nurse practitioners, consulting physicians (e.g. orthopedic surgeons) and others on the trauma care team. Up to 60 trauma care providers will participate in focus groups across the three sites. We will test the intervention with severely injured older adults at OHSU and UT-S/PMH. In the first year, UT-S/PMH and OHSU will recruit and enroll 50 patients total in the control arm and train trauma providers to use the best case/worst case tool. Trauma providers trained on the tool will be interviewed after training to explore their thoughts on how the tool works in their trauma unit. In the second year, UT-S/PMH and OHSU will recruit and enroll 50 patients total in the intervention arm. UW will compare survey-reported and chart-derived measures before and after clinicians learn to use the best case/worst case tool.

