Using our best case/worst case training program, a trainer at the UT-S/PMH and OHSU sites will train all consenting attending trauma surgeons and trauma team members. As part of the training, participants (estimated 15 participants per site, no more than 20) will participate in an assessment session, demonstrating their use of the tool with a standardized patient and scripted clinical scenario. Standardized patients for these teaching sessions will be hired at UT-S and OHSU and will not be study subjects (do not need to sign consent). In the second hour of the session, surgeons will practice these skills and use the communication tool with two standardized patients in audio recorded sessions. Surgeons will then receive immediate feedback and encouragement from an expert observer after each interaction with the standardized patient. UW research team members will assess the fidelity of participant use of the tool using an 11-item checklist of adherence criteria and give feedback until they achieve an acceptable level of competence. Training participants will be asked to participate in a one-time brief interview following the training to explore their thoughts on how the tool has worked/could work in their trauma unit.

As close as possible to 72 hours after injury, study staff at UT-S/PMH and OHSU will give the patient's primary nurse the clinician version of the QOC

Study staff at UT-S/PMH and OHSU will also archive a copy of the graphic aid that surgeons used with study-enrolled family members and patients. Study staff at UT-S/PMH and OHSU will give all trauma unit nurses and physicians the Moral Distress Scale-Revised (MDS-R)⁴⁴, physician and nurse versions at the start and end of the study.

There will be two groups of patient participants at UT-S/PMH and OHSU in this study:

Group A (control): Before the surgeon has been taught to use the best case/worst case tool, we will enroll patients and their family member. These patients will have been provided usual care.

Group B (intervention): After the surgeon has been taught to use the best case/worst case tool, patients and family members will be enrolled and will follow the same data collection schedule as for control patients. The study team will archive a copy of the "best case/worst case" graphic aids created by the surgeon in the intervention arm as well.

Training Program

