P1: Patient Survey (Only given to patients with DMC)	Survey given to patients with DMC	30 days post-admission	In-person (if patient member available in hospital) Telephone	T-QoL ⁴³
U1: Unit-wide moral distress survey (pre)	Start of study, prior to any patient enrollment	Before best case/worst case training	Anonymous paper survey	MDS-R ⁴⁴ Physician and nurse versions
U2: Unit-wide moral distress survey (post)	End of study, after all intervention patients are enrolled	After best case/worst case training	Anonymous paper survey	MDS-R Physician and nurse versions
Graphic aid photo-documentation	Graphic aid created by surgeon	As close as possible to 24-72 hours after admission	De-identified digital image	N/A

As shown below, research team members at UT-S/PMH and OHSU will administer 2-3 surveys to family member study partners (number dependent upon whether the patient is alive at 30 days). If the patient has DMC at 30 days, they will be contacted for a single survey.

Data Collection Administration

Focus groups:

A skilled focus group facilitator familiar with technical constructs relating to the topic area will lead the focus group discussions. Focus group discussions will last approximately 90 minutes and will include questions on the challenges providers face when talking with family members of older patients with serious traumatic injury about treatment and prognosis. The focus group moderator will also describe a hypothetical patient and ask focus group participants how they might discuss prognosis and treatment options with the patient's family. Participants will then watch a brief video depicting a surgeon describing treatment options to a patient using the best case/worst case communication technique. After viewing the video, the focus group moderator will ask attendees how best case/worst case could be used in their practice. Focus group guide questions are sample questions and in some cases the facilitator may ask follow up questions not included on the guide.

We will give focus group participants a brief exit survey to complete at the conclusion of the focus group. The exit survey will include demographic questions, as well as questions about the participant's professional role and training. The exit survey will not include collection of any identifiers.

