A member of the research team will check the patient's chart and, if needed, check with the care team to determine whether the patient is alive at 30 days and, if so, if they have DMC at that time. If patients are alive at 30 days and have DMC, they will be contacted by UT-S/PMH or OHSU research team members either in-person (if still receiving care in the hospital) or by phone (if they have been discharged), to complete the P1 survey. (If patients did not have DMC at the time of their family member enrollment but have regained it, as noted in their medical chart, they will be mailed a copy of the consent form or be consented in person if they remain hospitalized so that they may participate in the P1 survey.) The P1 survey consists of The Trauma Quality of Life (T-QoL)⁴³ survey. This 43-item survey is designed assess posttraumatic quality of life.

N1: Nurse survey

Research team members at UT-S/PMH and OHSU will give the N1 survey to the patient's primary nurse as close as possible to 72 hours after admission. The nurse-specific Quality of Communication (QOC) survey⁴⁰ is comprised of 18 items asking how well a provider talks with his or her patients about their care. Research team members at UT-S/PMH and OHSU will make multiple attempts to collect this data in person, 72 hours after admission, if the nurse is still on shift and in the clinic. If the nurse cannot be reached in person, research team members will reach out to them by email to complete a web version of the QOC.

U1: Unit-wide moral distress survey (pre-intervention) and U2: Unit-wide moral distress survey (post-intervention)

All trauma unit nurses and physicians at UT-S/PMH and OHSU will be invited to participate in this anonymous paper survey at two time points: at the start of the study (prior to any patient enrollment) and the end (after all study patients are enrolled). Research staff will approach trauma unit clinicians in person to invite them to complete a paper copy of this survey. The survey consists of the Moral Distress Scale-Revised (MDS-R)⁴⁴, physician and nurse versions. The survey describes brief descriptions of 21 situations which may occur in clinical practice, asking the frequency and level of disturbance that each situation causes.

Chart review

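### The moral distress baseline is taken before any control patient is enrolled, so the before/after-training change also spans the whole control phase, up to about a year

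*Combined protocol and SAP*

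**What the plan says.** **Purpose.** Project Summary and Timeline says that trauma unit staff will be surveyed "before and after clinicians learn to use the best case/worst case tool, to assess whether the communication intervention improves feelings of moral distress".

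**Survey timing.** The U1/U2 text under Data Collection Administration places the two surveys "at the start of the study (prior to any patient enrollment) and the end (after all study patients are enrolled"). The Instruments table agrees: U1 is "Start of study, prior to any patient enrollment" and U2 is "End of study, after all intervention patients are enrolled". Research Design has the MDS-R given in "physician and nurse versions at the start and end of the study". The table's administration column also describes U1 as before training. That is true, but it does not place U1 close to training.

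**Study timeline.** Project Summary and Timeline: "In the first year, UT-S/PMH and OHSU will recruit and enroll 50 patients total in the control arm and train trauma providers", and then "In the second year, UT-S/PMH and OHSU will recruit and enroll 50 patients total in the intervention arm". Research Design defines the control group this way: "Before the surgeon has been taught to use the best case/worst case tool, we will enroll patients and their family member". Sample Size confirms that the two arms are recruited in sequence.

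**Analysis and linkage.** The consent section makes the survey anonymous; returned forms carry only a sequential tally number. No section gives an MDS-R analysis, a time-trend adjustment or a comparison unit.

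**The concern.** The stated question is whether distress changes once clinicians learn the tool. The planned difference instead runs from a point before the study's patient work begins to its end. It covers three stretches: the control phase, training and the intervention phase. Only the last two can carry an effect of training.

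The control phase is not neutral for the people surveyed. Surgeons consent before it, knowing that families and nurses will rate their communication. Primary nurses of control patients complete a rating for each one. The protocol's own risk section accepts that being rated, and rating a colleague, may be stressful. If that shifts MDS-R scores, the shift enters U2 minus U1 as though the tool had caused it. The same holds for changes in staffing, case mix or unit policy during control enrollment, and for staff who leave or join.

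With two anonymous waves and no comparison unit, none of this can be separated afterwards. At stake is the reading of a secondary staff outcome.

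**Working it through.** The documents state no MDS-R sample size, standard deviation, effect size or expected change, so there is no planned figure to reproduce. The check is of the timeline, followed by what it implies for bias.

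**Step 1: order of events, from the documents.**
- U1 precedes every patient, including controls.
- Controls are enrolled before their surgeon is trained; control enrollment and training are both first-year activities.
- Intervention patients are enrolled in the second year, and U2 follows the last of them.

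The order is therefore U1, control phase, training, intervention phase, U2. No MDS-R wave falls between U1 and U2.

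**Step 2: share of the interval before training.** Assumptions: U1 at month 0, U2 at about month 24, training at month t with t = 6, 9 or 12. The documents put training in year one but give no month. Pre-training share = t/24.

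**Step 3: drift bias.** Suppose MDS-R drifts linearly by b points per year for reasons other than the tool (b may have either sign).
- Drift in U2 − U1 = b × 24/12 = 2.0b.
- Drift from a wave just before training to U2 = b × (24 − t)/12.

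| Training month t | Pre-training share | Drift, U1 baseline | Drift, pre-training baseline | Removed |
|---|---|---|---|---|
| 6 | 6/24 = 25% | 2.0b | 18/12 × b = 1.5b | 0.5b |
| 9 | 9/24 = 37.5% | 2.0b | 15/12 × b = 1.25b | 0.75b |
| 12 | 12/24 = 50% | 2.0b | 12/12 × b = 1.0b | 1.0b |

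Linearity matters. If all the drift fell in the control phase, the later baseline would remove all of it; if all fell after training, it would remove none.

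**Step 4: change in who is surveyed.** The documents give no turnover rate; assume r = 15% to 25% a year. The share of staff in post at baseline who have left by U2 is 1 − (1 − r)^years.
- From U1 (2 years): 1 − 0.85² = 28%; 1 − 0.75² = 44%.
- From a pre-training wave at month 6 (1.5 years): 1 − 0.85^1.5 = 22%; 1 − 0.75^1.5 = 35%.
- From a pre-training wave at month 12 (1 year): 15%; 25%.

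Because each wave invites the whole unit, turnover is a change in the mix of respondents and not simply lost baseline data.

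**The case against.** **An early baseline has value.** A wave before patient enrollment is untouched by the rating activity of the control phase. A later one may follow exposure to the tool itself: focus groups at both intervention sites include surgeons and ICU nurses, who watch a video of the tool being used. At two groups of five to ten per site, that is up to 20 people per site. This stands, and it is why the early wave should be kept if possible. It is qualified by the fact that the documents do not date the focus groups relative to U1, so they do not show that U1 is free of that exposure either.

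**The inference stays weak after the change.** This also stands. On the same assumptions, 12 to 18 months of uncontrolled time would remain between the new baseline and U2, so baseline placement limits drift but is not a full safeguard.

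**The switch from control to intervention may not be clean.** Training runs in sessions of two or three surgeons, with about 15 participants expected per site, so roughly five to eight sessions (15/3 = 5; 15/2 = 7.5). Arm membership depends on whether the particular surgeon has been taught. The first training session and the last control patient may therefore not coincide. This stands as a practical point: a new wave needs one anchor, and the first session is the one that guarantees no trained staff at baseline.

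**Stronger readings that do not hold.** A reader might infer that U1 is a full year before training, so that moving it halves the bias. That is the upper end: it needs training at month 12 and linear drift. The timeline figure and most of the Schedule of Events are not visible in the text available, so exact dates may exist there. A reader might also infer that the survey text contradicts its stated purpose. It does not: U1 is before training, only not close to it.

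**Conclusion.** The point holds, as a design weakness in a non-primary outcome. The order of events is explicit in the documents: the whole control phase lies between U1 and training, so U2 minus U1 cannot be read as the effect of learning the tool.

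The gap is up to about a year. The 25% to 50% pre-training share, and the fall in drift bias from about 2.0b to between 1.5b and 1.0b, rest on assumed months for training and U2 and on linear drift. The size of b is unknown, so the bias in MDS-R points cannot be stated.

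A reader might extend this to the main result. The documents do not support that: family-reported Quality of Communication is compared between control and intervention patients, and moving or adding an MDS-R wave changes nothing there.

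**What to change.** Amend Research Design, the U1 and U2 rows of the Instruments table, and the U1/U2 text under Data Collection Administration as follows.

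1. Give the MDS-R at each site immediately before that site's first training session, and name that wave as the baseline for the before/after-training comparison.
2. Keep the start-of-study wave. Its difference from the pre-training wave shows control-phase drift, and it gives a baseline from before patient enrollment. Leave U2 where it is.
3. If only two waves are feasible, place U1 just before the site's first training session.
4. If no pre-training wave can be taken, report U2 minus U1 as a descriptive start-to-end difference, not as an effect of the tool.
5. Record the dates of each wave, each training session and the focus groups by site, so that readers can see what each interval contains.

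**Cost.** One more round of a 21-situation anonymous paper form, with no incentive payment and the same staff, plus the protocol change. The downsides are some added respondent burden and the possibility that some staff have already seen the tool in a focus group by the time of the new baseline.
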